12.5.4.3.3 Impact of Major Important Protocol Deviations and Deviations from Predefined Time Windows

If more than 20% of patients from FAS are excluded in the PP Analysis Set; the robustness of the MAS scores results with regard to major IPDs will be assessed as described just above.

The change from baseline to D21 of each treatment period (as defined in [Section 10.2](#) and [Section 10.3](#)) in LLMT-6, LLMT-4 and LLMT-10 scores will be analyzed with a linear mixed-effects model for crossover data applied to MI datasets using the approach described in respectively [Section 12.5.2.1](#), [Section 12.5.3.1](#) and in [Section 12.5.4.1](#) during the 51-day randomized period using the PP Analysis Set.

Furthermore, to also assess the impact on deviation from predefined time window at D1H3, the change from baseline to D21 of each treatment period (as defined in [Section 10.2](#) and [Section 10.3](#)) in LLMT-6 score will be analyzed by means of a linear mixed-effects model with repeated measures for crossover data applied to MI dataset using the approach described in [Section 12.5.4.2](#), but during the 51-day on-treatment efficacy period. For this analysis any D1H3 MAS assessment not having taken place within 3 hours (\pm 15 minutes) post first morning dosing spray will be excluded from the analysis.

If more than 20% patients from FAS are excluded in the PP analysis set this analysis will be conducted on the PP analysis set, otherwise the FAS will be used.

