AE = adverse events; C-SSRS = Columbia-Suicide Severity Rating Scale; ECG = electrocardiogram; IMP = investigational medicinal product; MAS = Modified Ashworth Scale; MS = multiple sclerosis; MSSS-88 = Multiple Sclerosis Spasticity Scale; NRS = Numerical Rating Scale; PK = pharmacokinetics; T25FW = Timed 25-Foot Walk; THC = Δ^9 -tetrahydrocannabinol.

^a A washout period of at least 7 days will separate the 2 treatment periods. Following the final dose of IMP in Treatment Period 1, in the morning of Visit 5 (Day 21), patients will discontinue treatment with IMP for the 7 days prior to Visit 6 (Day 31). During the washout period, patients will continue to take their current MS antispasticity medications without any changes in dose.

^b A comprehensive physical examination, including an assessment of height, will be completed at Screening (Visit 1) only; subsequent physical examinations will be symptom-directed.

^c Serum pregnancy test at Visits 1 and 10; urine pregnancy test at Visits 2 and 6 (predose).

^d On the day before PK blood sampling at Visits 4, 5, 8, and 9, patients will be prompted to record whether they started their morning and evening doses of IMP within 30 minutes of a snack or meal. On the day of PK blood sampling, the exact time and date of PK blood sampling and the time of the patient's snacks and meals should be recorded. See **Section 9.2.12.1** for the PK blood sampling schedule. Please note that more than one PK sample may be collected at distinct time points during a single visit.

^e Patients will record their 11-point NRS spasticity score, spasm count, and use of antispasticity medications in an electronic diary once daily, around the same time each day, preferably in the evening before retiring to sleep, for at least 7 days prior to Visits 2 and 6 and throughout the trial until Visit 9. Investigational medicinal product dosing will be recorded by the patient in an electronic diary from Visits 2 through 9.

^f MAS assessments will occur at Visit 1 (Screening) and at scheduled time points before (Visits 2 and 6 [predose]) and after (Visits 2, 5, 6, and 9 [3 hours \pm 15 minutes postdose]) IMP administration; for Visits in which the morning dose consists of more than 1 spray (Visits 5 and 9), postdose assessments will occur 3 hours \pm 15 minutes after the first spray of the morning dose.

^g Non-ambulatory patients are not expected to perform the T25FW test.

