10.1.3 Target Days and Visit Window

Visit windows are summarized in [Table 10.1-3](#) for efficacy data and urine drug screen collection and, in [Table 10.1-2](#) for all other safety endpoints.

When there are multiple observations within a visit window, the value closest to the target day will be analyzed (as described in [Table 10.1-1](#)).

For safety assessments, on-treatment assessments will be preferred to off-treatment ones.

In case of ties between observations located on different sides of the target, the observation with the earliest date/time will be used. In case of ties between observations located on the same side of the target, (i.e., more than one value for the same day but at different time), the observation with the earliest date/time will be used. However, in case of non-respect of wash-out period, the one done at least 7 days after last Period 1 dosing date will be preferred.

For efficacy, PRO endpoints visit windowing will apply whether patient is on or off treatment.

Table 10.1-1 Longitudinal Assessment – Analysis Day and Target Day

Treatment Period	Visit / Day	Analysis visit	Target Day (defined by period)	Observation used for analysis, if more than one exists
Screening	Visit 1 / Day -28 to -1	Screening	Day -28 to -1	Latest value
Period 1	Visit 2 / Day 1	Day 1	Day 1*	Closest to Target Day But Day 1 H0 should be before 1 st IMP intake and D1H3 should be post IMP intake
	Visit 3 / Day 8	Day 8	Day 8	Closest to Target Day
	Visit 4 / Day 15	Day 15	Day 15	Closest to Target Day
	Visit 5 / D21	D21	D21	Closest to Target Day
Period 2	Visit 6 / Day 31	Day 1	Day 1*	Closest to Target Day But Day 1 H0 should be before 1 st IMP intake and

Treatment Period	Visit / Day	Analysis visit	Target Day (defined by period)	Observation used for analysis, if more than one exists
				D1H3 should be post IMP intake.
	Visit 7 / Day 38	Day 8	Day 8	Closest to Target Day
	Visit 8 / Day 45	Day 15	Day 15	Closest to Target Day
	Visit 9 / Day 51	D21	D21	Closest to Target Day
Follow-up	Visit 10 / Day 58	Day 28	Day 28**	Closest to Target Day

H = Hours; IMP = Investigational medical product.

** Day 1 is based on the date of IRT call within each period*

*** Day 28 relative to the period where IMP is permanently discontinued thus visit is expected between Day 25 and Day 31*

Table 10.1-2 Longitudinal Assessment – Target Day and Visit Window – Part 1

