	Visit 5 / D21	D21***		Day 19 up to LP1V	Day 19 up to LP1V	Day 1 post dose of 1 st IMP intake up to LP1V	Day 1 post dose of 1 st IMP intake up to LP1V
Wash out period							
Period 2	Visit 6 / Day 31	Day 1H0*		Day 1 – 4 days to D1H0 *	Day 1H0 (before P2 IMP intake)	Day 1H0 (before P2 IMP intake)	Day 1H0 (before P2 IMP intake)
	Visit 6 / Day 31	Day 1H2- H4**			Day 1 post dose (the day of 1 st P2 IMP intake)** up to Day 18		
	Visit 8 / Day 45	Day 15		Day 2 (day following IMP intake) – Day 18 (or the first day of maintenance phase)			
	Visit 9 / Day 51	D21***		Day 19 to LP2V	Day 19 to LP2V	Day 1 post dose of Period 2 1 st IMP intake up to LP2V	Day 1 post dose of Period 2 1 st IMP intake up to LP2V
Follow-up	Visit 10 / Day 58	Day 28****		After last IMP dosing			

H = Hours, P = Period; LP1V = Last visit during Period 1, LP2V = Last visit during Period 2, IMP = Investigational Medicinal Product, NRS = Numerical Rating Scale; IRT = Interactive Response System, MAS = Modified Ashworth Scale, MSSS-88 = Multiple Sclerosis Spasticity Scale; T25FW = Timed 25-Foot Walk.

* Day 1 is based on the date of IRT call within each period.

** D1H2-H4 for sensitivity analysis purpose only assessments collected between at H3 (+/- 15 min) post first IMP morning spray will be considered. Should be collected during the titration phase

*** D21 should be collected during the maintenance phase (including off-treatment days).

**** Day 28 relative to the period where IMP is permanently discontinued.

For patient electronic diary-based endpoints (NRS-spasticity and spasm count), baseline is defined as the weekly average of daily electronic diary entries over the last 7 days prior to randomization (Visit 2, Period 1 Day 1H0).

In case of missing assessments within the 7 days preceding Period1 Day1 H0

- For 11-point NRS spasticity scale, the weekly average will be set to missing if scores are missing for 4 days in total or for 3 consecutive days within the 7-days period.
- For daily spasm count, the weekly average will be derived as detailed in [Section 10.19](#) and will be set to missing if spasm count is not collected during 4 days out of 7 or for 3 consecutive days during the last 7 days preceding Day 1H0.

For clinic-efficacy based endpoints, baseline is defined as the last record or measure collected prior to the first dose of IMP in each treatment period.

However, if deemed necessary the baseline will be defined for each period as described in [Section 10.1.2](#) as:

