	P1, SUP7 (Supplementary without major IPD impact)	Variable: Change from period baseline in LLMT-6 at D21 Population: PP analysis set IES: Regardless permanent treatment discontinuation Prior to major IPD Accounting for COVID-19 impact PLS: Mean difference between nabiximols and placebo Analysis: LSMD from CFB linear mixed-effect model for crossover data adjusted on period baseline LLMT-6 with placebo-based MI under MNAR assumption.
	P1, SUP8 (Supplementary without major IPD impact and without deviation from time window)	Variable: Change from period baseline in LLMT-6 at D21 Population: PP analysis set IES: Prior permanent treatment discontinuation Regardless premature study discontinuation Without major IPD Without deviation from time window at D1H3 Accounting for COVID-19 impact PLS: Mean difference between nabiximols and placebo Analysis: LSMD from CFB linear mixed-effect model with repeated measure for crossover data adjusted on period baseline LLMT-6 with placebo-based MI under MNAR assumption.
	P1, SUP9 (Supplementary without COVID-19 impact)	Variable: Change from period baseline in LLMT-6 at D21 Population: FAS IES: Regardless permanent treatment discontinuation Regardless premature study discontinuation Regardless major IPD Without COVID-19 impact PLS: Mean difference between nabiximols and placebo Analysis: LSMD from CFB linear mixed-effect model for crossover data adjusted on period baseline LLMT-6 with placebo-based MI under MNAR assumption.
LLMT-4	S1, Primary	Variable: Change from period baseline in LLMT-4 at D21 Population: FAS IES: Regardless permanent treatment discontinuation Regardless premature study discontinuation Regardless major IPD Accounting for COVID-19 impact PLS: Mean difference between nabiximols and placebo Analysis: LSMD from CFB linear mixed-effect model for crossover data adjusted on period baseline LLMT-4 with placebo-based MI under MNAR assumption.

Secondary objective (efficacy): To evaluate the effect of multiple doses of nabiximols as adjunctive therapy compared with placebo on a clinical measure of velocity-dependent muscle tone in the lower limbs (Lower Limb Muscle Tone 4; LLMT-4) in patients with multiple sclerosis who have not achieved adequate relief from spasticity with other antispasticity medications.

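### The SAP's only hour-level timing check covers D1H3; the primary-endpoint D21 MAS score is accepted whatever its hour, and same-day repeats resolve to the earliest

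*SAP*

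**What the plan says.** **Collection.** Protocol 9.1.2.3 and 9.1.4.3 schedule one MAS at each of Visits 5 and 9, timed from the first morning spray, and none before the dose. Footnote f of protocol Appendix 1 agrees: "Visits 5 and 9), postdose assessments will occur 3 hours" ± 15 minutes after that spray. The SAP repeats this under its schedule of assessments in 8.1.

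**Selecting the D21 score.** SAP Table 10.1-3 takes any Period 1 MAS from "Day 19 up to LP1V" (LP1V is the last Period 1 visit), with a matching window in Period 2. The D21 footnote adds only: "D21 should be collected during the maintenance phase (including off-treatment days"). Table 10.1-1 requires the predose and 3-hour scores to fall on the correct side of the dose on the first day of each period. Its D21 row asks only for nearness to the target day. For same-day values, 10.1.3 says: "more than one value for the same day but at different time), the observation with the earliest date/time will be used".

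**Hour-level check.** The Table 10.1-3 footnote for the first-day post-dose score reads: "D1H2-H4 for sensitivity analysis purpose only assessments collected between at H3 (+/- 15 min) post first IMP morning spray will be considered". Section 12.5.4.3.3 states its timing aim as "to also assess the impact on deviation from predefined time window at D1H3", and its exclusion rule begins "For this analysis any D1H3 MAS assessment not having taken place within 3 hours" (± 15 minutes) of the first morning spray. SUP8 in Appendix 14 is defined as "Without deviation from time window at D1H3".

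**The concern.** The primary endpoint is the change from period baseline to D21, measured at a fixed time after the morning dose. The 12.5.4.3.3 timing analysis also reports change to D21, but the only scores it screens by hour are D1H3 scores. D1H3 follows the single spray that opens each period. It enters the primary analysis only as a predictor in the imputation models (SAP 12.5.2.1.6). Removing mistimed D1H3 scores therefore cannot show whether the D21 result is robust to D21 timing.

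The tie rule raises a second issue. Patients arrive at Visits 5 and 9 without having taken their morning dose (protocol 4.1). If a site scores early and then repeats at the scheduled time, the SAP keeps the early score and discards the compliant one. On the first day of a period Table 10.1-1 guards against a wrong-side score; on D21 nothing does.

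**Working it through.** **1. The rules side by side**

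| Rule | D1H3 | D21 (primary) |
|---|---|---|
| Scheduled time | 3 h ± 15 min post-dose | 3 h ± 15 min after first morning spray |
| Analysis window (SAP Table 10.1-3) | First day post-dose up to Day 18 | Day 19 to last visit of the period |
| Pre/post-dose condition (SAP Table 10.1-1) | Yes | No |
| Hour filter in any analysis | Yes (12.5.4.3.3, SUP8) | No |
| Same-day repeats (SAP 10.1.3) | Earliest, but must be post-dose | Earliest, no condition |

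SAP Appendix 1 lists 32 major deviations. Three come near the point. Item 12 is a missed morning spray on the last maintenance day, which concerns dosing and not MAS time. Item 19 is a missing evaluable LLMT-6 at endpoint, with evaluable left undefined. Item 22 gives visit limits in days. None states a post-dose hour.

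**2. The tie rule applied.** Suppose a site scores a patient on arrival at Visit 5 and again 3 h after the first spray. Both scores fall on the same day, so neither is nearer the target day. The rule selects the arrival score, which is predose.

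**3. What a bare D21 filter would do.** A dropped D1H3 score is an intermittent gap and is filled under missing at random (MAR; SAP 12.5.2.1.5). A dropped D21 score would fall under Table 12.5-1. There, missing data unrelated to COVID-19 in the nabiximols/placebo sequence, for a patient who stays in the study, go to control-based imputation; the placebo/nabiximols sequence goes to within-arm MAR. Dropped Period 1 nabiximols scores would be replaced by placebo-like values, so the result would mix timing with an imputation penalty.

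**4. Design figures reproduced.** Inputs from protocol 13.1: difference 0.30 (absolute), SD of paired differences 0.71, two-sided 5%. The noncentrality of the paired t-test is (0.30/0.71) × √n.
- n = 46: 0.4225 × 6.782 = 2.87, power 0.801, matching the stated 80%.
- 46/0.90 = 51.1, rounded up to 52, as stated.
- n = 68 (SAP 8.2): 0.4225 × 8.246 = 3.48, power 0.930, matching the stated figure above 90%.

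**5. Illustration only.** Assume a share f of nabiximols D21 scores is mistimed and loses a fraction l of the effect, with the SD unchanged. Neither f nor l is in the documents. The diluted difference is 0.30 × (1 − f × l).

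| f | l | Difference | Power, n = 46 | Power, n = 68 |
|---|---|---|---|---|
| 5% | 50% | 0.2925 | 0.781 | 0.917 |
| 5% | 100% | 0.285 | 0.759 | 0.904 |
| 10% | 50% | 0.285 | 0.759 | 0.904 |
| 10% | 100% | 0.270 | 0.714 | 0.871 |
| 20% | 50% | 0.270 | 0.714 | 0.871 |
| 20% | 100% | 0.240 | 0.612 | 0.784 |

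The l = 100% rows are an extreme: they suppose that about 20 days of dosing leave no effect at the moment of scoring.

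**The case against.** Much of the case on the other side stands.

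- A reader might infer that the D21 MAS can be taken at any hour. It cannot: both documents fix the time, and the dose is given on site under supervision. What is absent is an analysis rule, not a collection rule.
- A reader might infer that predose scores will routinely become the endpoint. No predose MAS is planned at Visits 5 and 9, so this needs an unscheduled or mistimed assessment. Nothing in the documents suggests that this is common, and the tie rule is a generic one.
- A reader might object to mistimed scores in the primary model. The primary estimand (SAP Table 9.1-2) handles other protocol deviations by treatment policy, so keeping them there is consistent with the plan.
- A reader might infer that mistimed D21 scores certainly stay in the per-protocol set. The listed criteria would not remove them, but evaluable is undefined, the important deviations are defined in separate guidance, and SAP 12.4 allows criteria to be adjusted before lock. The documents do not settle this.
- The D1H3 analysis does what its stated aim says. The section heading is broader than the analysis beneath it.

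What remains is that no pre-specified analysis tests D21 timing, and that a written rule would prefer a non-compliant same-day D21 score to a compliant one. The possibility of a discretionary blinded adjustment does not replace either.

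**Conclusion.** The point holds as a gap between the scheduled D21 time and the analysis rules. D21 scores are accepted whatever their hour, the only hour-level sensitivity analysis screens a timepoint that is not the primary endpoint, and same-day D21 repeats resolve to the earliest even if it is predose.

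The size cannot be estimated, because the documents do not say how often mistiming or repeats occur or how much effect a mistimed score loses. The dilution table rests wholly on assumed values and describes what a D21 timing analysis would look for. It is not a predicted bias. Every row moves toward no effect, so the documents give no support for inferring inflated benefit or type I error. No stated design figure changes. This is a cheap improvement and does not undermine the primary analysis.

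**What to change.** Before unblinding:

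1. In SAP Table 10.1-1 and the tie rule of 10.1.3, state that for patients dosed that morning the Visit 5 or Visit 9 D21 score is the post-dose score, and that same-day repeats resolve to the one nearest 3 h after the first spray.
2. Add a supplementary analysis of the primary D21 model, and extend SUP8 likewise, excluding D21 scores outside 3 h ± 15 min for patients dosed that morning. Handle the excluded scores under within-arm MAR, or leave them missing in the likelihood-based model. Do not send them through the control-based rule of Table 12.5-1.

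The primary estimand and data collection stay as they are. The cost is SAP wording and one further supplementary run, with fewer observed scores in that run. It relies on MAS and first-spray times being recorded at Visits 5 and 9, which should be confirmed; the D1H3 check already needs the same times on the first day of each period.

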12.5.4.3.4 Impact of COVID-19

If at least 5 patients have at least one visit where MAS scores are impacted by COVID-19, as assessed by the investigator, the impact of COVID-19 on the treatment effect will be assessed on MAS scores as described just below.

The change from baseline to D21 of each treatment period (as defined in [Sections 10.2 and 10.3](#)) in LLMT-6, LLMT-4 and LLMT-10 scores will be analyzed by the mean of a linear mixed-effects model for crossover data applied on MI datasets using the approach described respectively in [Section 12.5.2.1](#), [Section 12.5.3.1](#) and in [Section 12.5.4.1](#) but removing the patients having at least one MAS assessment impacted by COVID-19.

12.5.4.4 Other Summaries and Listings based on MAS

An histogram presenting combined LS mean change from baseline to D21 estimates in LLMT-6, LLMT-4 and LLMT-10 along with their corresponding 95% CIs will be provided by treatment arm using combined LS means and 95% CIs coming from the linear mixed-effects model for crossover data applied to MI datasets used to analyze these 3 efficacy endpoints (as respectively described in [Section 12.5.2.1](#), [Section 12.5.3.1](#) and [Section 12.5.4.1](#)).

Descriptive statistics will be provided for each of the 10 individual muscle group MAS scores, presenting observed values along with change from baseline and percentage change from baseline score per treatment arm by treatment period and overall.

A by-patient listing will be provided for observed and derived variables presenting each of the 10 individual MAS scores along with LLMT-4, LLMT-6 and LLMT-10 scores.

12.5.5 Exploratory Efficacy Analysis

All exploratory efficacy analyses will be conducted among the full analysis set during the 51-day efficacy randomized period.

If more than 20% of patients from FAS are excluded in the PP Analysis Set; the analyses may be repeated using the PP analysis set as described in [Section 12.5](#).

The exploratory efficacy analyses based on LLMT-10 are described in [Section 12.5.5](#).

If at least 5 patients have at least one visit where the studied endpoint is impacted by the COVID-19, as assessed by the investigator, the analysis of that endpoint will be repeated excluding the concerned patients as described below:

- For the average 25-foot walk time (as described in [Section 10.2](#) and in [Section 10.17](#)) if during Period 1 and/or Period 2, D21 visit, T25FW trials are impacted by COVID-19,
- For the 7-day average NRS spasticity score (as described in [Section 10.2](#) and in [Section 10.18](#)) if during Period 1 and/or Period 2, Day 15 or D21 visits are impacted by COVID-19 and patient is infected*,
- For the 7-days average daily spasm counts (as described in [Section 10.2](#) and in [Section 10.19](#)) if during Period 1 and/or Period 2, Day 15 or D21 visits are impacted by COVID-19 and patient is infected*,
- For MSSS-88 total and sub-scales scores (as described in [Section 10.20](#)) if during Period 1 and/or Period 2 at D21 Visit MSSS-88 scoring is impacted by COVID-19.

* For eDiary endpoints, impact on COVID-19 is assessed based on information collected on the "Visit COVID-19 Impact" eCRF form. Thus if reason is due to "Caregiver or family member infected with COVID-19" but not to "Patient infected by COVID-19" the assessment will not be discarded.

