10.3 Change from Baseline

Change from baseline (CFB) will be calculated as:

$$(\text{post-baseline} - \text{baseline}).$$

CFB will be calculated for patients with both a baseline and post-baseline value as applicable.

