10.17 Timed 25-Foot Walk

The T25FW is the time needed for a patient to walk 25-feet and will be performed at Day 1 H0 and D21 of each treatment period. The test consists of two trials separated by a 5-minute rest period. The maximum duration of each trial is set to 3 minutes (180 seconds).

The average T25FW (expressed in seconds) will be derived for each patient as the average of the two trials..

If a patient only performs 1 of the 2 trials at a given analysis day, the unperformed trial will be imputed using the highest T25FW (180 seconds) to perform the main analysis. An exploratory analysis will also be conducted without imputing unperformed trial as missing thus, leading to a missing average T25FW.

If a patient is not using the same device or is introducing a device within a given treatment period, the average T25FW will be set to missing.

The change and percentage change from baseline will then be calculated (as respectively described in [Section 10.3](#) and in [Section 10.4](#)).

The percentage change from baseline will be categorized as $\leq -20\%$ and $> -20\%$ to assess respectively $\geq 20\%$ improvement (as response) and $< 20\%$ improvement (as non-response) using imputed T25FW (as described above).

Missing average T25FW will be considered as not having met the improvement criteria (imputed as failure).

10.18 11-point Numerical Rating Scale Score (NRS-Spasticity Score)

The 7-day average 11-point NRS spasticity score will be derived for each patient as the mean NRS-spasticity score recorded in the eDiary during the last 7 days preceding Period 1 Day 1 H0 (Baseline), and Day 15 and D21 of each treatment period as follows:

Sum of the NRS spasticity scores during the 7 – day period

Number of days in which the daily diary was completed during the 7 – day period

For each assessment timepoint, the 7-day average 11-point NRS-spasticity score will be set to missing if scores are missing for 4 days or more in total or for 3 consecutive days within each 7-day period.

In case of the diary data are available but the visit does not take place the target visit date will be used.

On-treatment / off-treatment assessment

A 7-day average 11-point NRS spasticity score will be considered on-treatment if derived using only post baseline daily scores collected on or before the date of IMP discontinuation and will be considered off-treatment otherwise.

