12.5.5.1 Timed 25-Foot Walk (T25FW)

A decrease in average time to complete the two trials will show an improvement.

The difference between treatment arms in the change from baseline to D21 in average 25-foot walk time (as defined in [Section 10.17](#)) will be analyzed using the same LME model for crossover data as the one used for the primary analysis of the primary efficacy endpoint (as described in [Section 12.5.2.1.8](#)). As a sensitivity analysis, the same analysis will be repeated using non-imputed average 25-foot walk times (as defined in [Section 10.17](#)).

If model diagnostics suggests that the residuals are not normally distributed a non-parametric analysis will be conducted.

A $\geq 20\%$ reduction from baseline to D21 of in average time (as described in [Section 10.17](#)) will be analyzed using a logistic regression applied to crossover design using a GEE (as described in [Section 12.5.2.3.2](#)).

A histogram presenting LS means change from baseline estimates along with their corresponding 95% CI will be provided by treatment arm.

Descriptive statistics for the average T25FW values change from baseline and percentage change from baseline by treatment arm will be provided; as well as a by-patient listing presenting observed and derived variables.

12.5.5.2 11-point Numerical Rating Scale Score (NRS-spasticity score)

The 11-point NRS spasticity scale is composed of 11 items ranging from 0 (no spasticity) to 10 (maximal spasticity) to assess the overall spasticity in patients with MS during the last 24 hours.

The difference between treatment arms in the 7-day average NRS spasticity score over the last 7 day preceding D21 of each period (as defined in [Section 10.18](#)) will be analyzed using a linear mixed model for crossover data using the SAS® GLIMMIX procedure with an identity link function and a normal distribution. The 7-day average NRS spasticity D21 score will be included as the dependent variable. Hence, each patient will contribute two measurements to the model, one for each period of the study.

The preferred model will include period level treatment arm, treatment period, and treatment sequence as fixed effects. Unstructured (UN) covariance structure will be used to model the repeated 7-day average NRS spasticity scores. The denominator degrees of freedom will be calculated according to Kenward-Roger method (e.g., KR2, 2009 version).

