	E2, SUP1 (response analysis)	
Variable: proportion of patients with a 20% decrease from period baseline in average T25FW at D21
 
Population: FAS
 
IES:
 
 Regardless permanent treatment discontinuation Regardless premature study discontinuation Regardless major IPD Regardless COVID-19 impact 
PLS: Odd ratio in nabiximols versus placebo
 
Analysis: OR from logistic regression model for crossover data adjusted on period baseline average T25FW. Single imputation: Missing D21 values are imputed a failure.

	E2, SUP2 (Supplementary without major IPD impact)	
Variable: Change from period baseline in average 25-foot walk time at D21
 
Population: PP analysis set
 
IES:
 
 Regardless permanent treatment discontinuation Regardless premature study discontinuation Without major IPD Regardless COVID-19 impact 
PLS: Mean difference between nabiximols and placebo
 
Analysis: LSMD from CFB linear mixed-effect model for crossover data adjusted on period baseline average T25FW. No imputation under MAR assumption

	E2, SUP3 (Supplementary without COVID-19 impact)	
Variable: Change from period baseline in average 25-foot walk time at D21
 
Population: FAS
 
IES:
 
 Regardless permanent treatment discontinuation Regardless premature study discontinuation Regardless major IPD Without COVID-19 impact. 
PLS: Mean difference between nabiximols and placebo
 
Analysis: LSMD from CFB linear mixed-effect model for crossover data adjusted on period baseline average T25FW. No imputation under MAR assumption

Exploratory Objectives: To evaluate the effect of nabiximols after administration of multiple doses on the following patient-reported outcomes: the 11-point Numerical Rating Scale (NRS) spasticity score, Daily spasm count as well as the MS Spasticity Scale (MSSS-88) total and subdomain scores.

11-point NRS-spasticity score	E3, Primary	Variable: 7-day average NSR spasticity score at D21 Population: FAS IES: Regardless permanent treatment discontinuation Regardless premature study discontinuation Regardless major IPD Regardless COVID-19 impact PLS: Mean difference between nabiximols and placebo Analysis: LSMD from observed value linear mixed-effect model for crossover data. No imputation under MAR assumption

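### The T25FW analysis labelled as without COVID-19 impact excludes patients only for an affected Day 21 walk, so COVID-affected baseline walks stay in the change score

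*SAP*

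**What the plan says.** SAP Section 12.5.5 provides a COVID-19 repeat analysis for the exploratory efficacy endpoints. The trigger is general: "If at least 5 patients have at least one visit where the studied endpoint is impacted by the COVID-19", as judged by the investigator. Each endpoint then has its own condition for leaving patients out. For T25FW a patient is left out "if during Period 1 and/or Period 2, D21 visit, T25FW trials are impacted by COVID-19". The predose walk is not named for either period.

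Section 12.5.5.1 analyses the difference between arms "in the change from baseline to D21 in average 25-foot walk time". Section 10.17 says the test "will be performed at Day 1 H0 and D21 of each treatment period". For clinic-based efficacy endpoints, "baseline is defined as the last record or measure collected prior to the first dose of IMP in each treatment period", so each patient has two baseline walks, at Visit 2 and Visit 6. Under Section 10.3 the change is the later value minus the baseline, and "CFB will be calculated for patients with both a baseline and post-baseline value as applicable".

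Appendix 14 lists the repeat analysis (E2, SUP3) as "Supplementary without COVID-19 impact". For the MAS change scores, Section 12.5.4.3.4 plans the equivalent analysis by "removing the patients having at least one MAS assessment impacted by COVID-19".

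**The concern.** A T25FW change score is made from two walks, and the exclusion rule looks at one of them. If COVID-19 slows the baseline walk and the patient has recovered by D21, the change is negative, which the SAP reads as improvement, and the patient stays in.

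This can happen within the trial's rules. Protocol Section 10 lists a positive COVID-19 test after randomization as a reason for which treatment may be stopped at the investigator's discretion, with the patient remaining in the trial. An infection in the washout (Days 22 to 30) falls just before the Visit 6 baseline walk.

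The repeat analysis exists only to show the walking result with COVID-affected data taken out. A reader of the study report will take its label at face value.

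**Working it through.** The plan gives no figure on this point, so there is none to reproduce. The check sets the rules side by side and then illustrates the consequence with assumed walk times.

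**1. What is analysed and what is checked**

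| Endpoint (SAP section) | Outcome analysed | Assessments checked for COVID-19 |
|---|---|---|
| T25FW (12.5.5, 12.5.5.1) | D21 minus predose, with period baseline as covariate | D21 only |
| NRS and spasm count (12.5.5, 12.5.5.2, 12.5.5.3) | End-of-period average, no baseline term | Day 15 or D21 |
| MSSS-88 (12.5.5, 12.5.5.4) | D21 score, no baseline term | D21 |
| LLMT-6, LLMT-4, LLMT-10 (12.5.4.3.4) | D21 minus predose, with period baseline as covariate | Any MAS assessment |

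T25FW is the only endpoint in the 12.5.5 list analysed as a change from baseline. Checking post-baseline visits alone suits its neighbours but not T25FW.

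**2. One patient, no true change**

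Let the usual time be T, the baseline walk T(1 + f), and the D21 walk T. The change is −fT and the percentage change is −100·f/(1 + f). T = 10 s (range 8 to 15 s) is assumed.

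| Slowing f | Change at T = 10 s (T = 8 to 15 s) | Percentage change |
|---|---|---|
| 10% | −1.0 s (−0.8 to −1.5) | −9.1% |
| 25% | −2.5 s (−2.0 to −3.75) | −20.0% |
| 50% | −5.0 s (−4.0 to −7.5) | −33.3% |

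Section 10.17 counts −20% or lower as a response. Solving f/(1 + f) ≥ 0.20 gives f ≥ 0.25, whatever T is.

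**3. The treatment difference**

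Without covariates, the nabiximols-placebo estimate is half the between-sequence difference in the mean of (Period 2 change − Period 1 change). With n walkers per sequence, a baseline slowed by s seconds in one patient moves it by s/(2n). Taking the 68 completers of SAP Section 8.2, equally split and all walking, n = 34 and the shift is s/68. For five patients in one sequence this is 5 × 2.5/68 = 0.18 s, or 5 × 5/68 = 0.37 s. With a 2:3 split only one patient is unbalanced: 2.5/68 = 0.04 s, or 5/68 = 0.07 s.

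A simulation with no treatment effect added baseline adjustment (68 patients, assumed mean 10 s, between-patient SD 3 s, within-patient SD 1 s, 400 replicates, Period 2 baselines slowed). Negative values favour nabiximols.

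| Affected, placebo/nabiximols : nabiximols/placebo | Slowing | No adjustment | Pooled baseline covariate | Within-patient adjustment |
|---|---|---|---|---|
| 5 : 0 | 2.5 s | −0.173 | −0.152 | 0.000 |
| 5 : 0 | 5 s | −0.357 | −0.293 | 0.015 |
| 3 : 2 | 2.5 s | −0.046 | −0.042 | −0.009 |
| 3 : 2 | 5 s | −0.065 | −0.054 | −0.001 |
| 0 : 5 | 2.5 s | 0.183 | 0.161 | −0.003 |
| 0 : 5 | 5 s | 0.367 | 0.305 | 0.002 |

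Neither adjusted column is exactly the planned mixed model. They show how far the result depends on the way the baseline covariate acts.

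**The case against.** The strongest counter-argument is that this hardly matters. The endpoint is exploratory and outside the testing hierarchy, and the analysis is supplementary and conditional. The model adjusts for the period baseline. SAP Section 12.7.5.7 lists patients affected by COVID-19, and Section 12.5.5.1 lists T25FW values by patient, so an affected baseline could be traced.

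The scenario is also narrow. Patients who stop treatment in Period 1 contribute no Period 2 data, visit windows may be extended for infection (Protocol Section 9), and with no baseline value no change is calculated. Section 12.5 also mentions, among analyses that may be done, leaving out patients with any COVID-affected efficacy assessment. All of this stands and keeps the point small. The Section 12.5 statement is optional, however, and does not override the specific T25FW bullet.

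A reader might infer more than the documents support:

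- *That the analysis is biased towards nabiximols.* The individual change score leans towards improvement, but the credit goes to whichever treatment follows the affected baseline. A slowed Visit 6 walk favours nabiximols in one sequence and placebo in the other, and balanced cases largely cancel.
- *That the SAP contradicts itself.* The MAS and T25FW rules sit in different sections and govern different endpoints. The difference is one of approach.
- *That the five-patient trigger also misses baseline walks.* It counts an impact at any visit. A patient affected only at baseline can help start the analysis and still not be removed by it.
- *That an unperformed baseline trial set to 180 s would produce enormous false improvements here.* Section 10.17 uses that imputation for the main analysis, but Appendix 14 lists this repeat as having no imputation, so it is not counted.

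**Conclusion.** The point holds as a mismatch between a rule and its label. Section 12.5.5 removes affected D21 walks but leaves affected baseline walks in a change-score analysis presented as free of COVID-19 impact. For the individual patient the distortion is definite: a baseline slowed by 25% or more yields a 20% improvement with no real change. Appendix 14 lists only the change-score version of this repeat, so the responder threshold serves here as a yardstick.

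For the nabiximols-placebo difference, neither direction nor size can be determined, because the documents give no count of affected walks. Under the assumptions shown it is about 0.15 to 0.37 s with all five patients in one sequence (pooled adjustment or none), under 0.1 s with a 2:3 split, and near zero with fully within-patient adjustment. Non-ambulatory patients are not expected to walk, so the true n may be below 34; the unadjusted shift grows in proportion to 1/n. The primary and secondary conclusions are not touched.

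**What to change.** In the T25FW bullet of SAP Section 12.5.5, leave a patient out when COVID-19 affected the T25FW trials at Day 1 H0 or at D21 in either period. This brings the rule into line with Section 12.5.4.3.4 and makes the analysis fit its Appendix 14 label. The five-patient trigger needs no change.

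The cost is one phrase, and possibly a few more patients left out of a conditional supplementary analysis of an exploratory endpoint.
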